1-3 hours	Support for subject and integration of experience
3 hours	BP, HR, Second Pump
3-6 hours	Subject relaxing at Study Site
6 hours	Third Pump
9 hours	Fourth Pump
12 hours	Fifth Pump if necessary (as per procedure)
Home	Milk has been quantified for volume at each pump and an aliquot labelled, saved and refrigerated. If subject has gone home earlier—at 6 hours or later, subject will be contacted to pump at the assigned intervals and an aliquot refrigerated for pickup and delivery to the clinical lab for analysis.

Safety: Administration of ketamine will occur in office premises and with standard of care safety equipment available. This includes CPR trained personnel, ambu bag, defibrillator and a suction device. MDs will be present on site throughout and will administer the injections.

Injections are provided with a 25 gauge, 1 inch needle using ketamine in a sterile 100mg/ml concentration. Total volume of ketamine fluid will be less than 1 cc. Occasionally, there may be a slight bleed from the injection site. There may be mild ache at the injection site for up to a few hours. Injections are intra-muscular and into the deltoid or buttocks regions.

Subjects will be provided in advance for preliminary screening with our standard intake form to assess current and previous illnesses, psychiatric conditions, and emergency contacts, etc. This will enable Investigators to screen potential subjects prior to enrollment—as is our general practice. The Informed Consent will be provided along with the Intake Form for review by the subjects prior to making a decision to proceed with the study intake process.

At Intake, subjects will discuss, and make a decision to sign, or , the Informed Consent.

HIPAA confidentiality will be maintained throughout. Subjects will be given a numerical designation for all materials, other than the written forms discussed herein. All written and confidential materials will be stored in a locked file on premises available only to the Investigators.

No hazardous substances or procedures are involved

Methods

Quantitative analysis of ketamine will be performed by [name] PhD, Professor of Laboratory Medicine at UCSF School of Medicine and [name] at UCSF.

- 1) Lab will prepare a standard for analysis of ketamine and its principle metabolite norketamine in breast milk. The half-life of ketamine is 2.1 hours, and that of norketamine 1.2 hours (Herd et al 2007). The study will view the half-life as being a conservative 3 hours.

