Subjects will refrain from eating and drinking 3-4 hours before receiving ketamine, this to

prevent stomach contents that may contribute to nausea, and reduce any risk of aspiration. Subjects are permitted one cup of coffee, juice or water at 3-4 hours prior if they are caffeine dependent. PROVIDED IN LAST VERSION

- 1) A urine pregnancy test will be conducted prior to each administration of ketamine.
- 1)
- 2) A first subject in the study will have milk collected at 0, 3, 6, 9, 12 and 15 hours to determine if these intervals are sufficient to characterize a basic pharmacodynamic profile. If there is a negligible quantity in the samples as the time frame proceeds, the lab will not analyze subsequent samples. Once determined, the study will proceed with the remaining 3 subjects at the intervals projected from the first subject. The lab will process the samples from the first subject as rapidly as possible to enable continuation of the study. Breast milk will be collected until ketamine levels are undetectable. If significant amounts of ketamine are found in samples from the 3 subsequent subjects at the last interval determined by the profile of the first subject, additional time frames for collection will be added. If necessary, the process will be repeated to fully document pharmacokinetics.

As real time testing of ketamine content in breastmilk is not possible, the first subject will be the exemplar for the timing of the resumption of breast feeding based on the data obtained, such as not detectable at 9 hours, hence breast feeding may resume. For that first subject, breast feeding may resume at 18 hours, which corresponds to 9 half-lives for ketamine, 4 half-lives being the accepted timing for the absence of a molecule. This will be confirmed by lab testing as quickly as possible for the first subject.

- 3) Pumping of breast milk will be for a full expression so as not to influence concentrations in subsequent sampling intervals. The volume of breast milk will be quantified for each expression.
- 4) Milk will be refrigerated in sterile containers and aliquots of one ounce will be brought to the lab refrigerated as soon as possible. A second aliquot of each

expression will be frozen in the event of loss or spoilage of the first aliquots, site to be determined.

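### Subjects 2–4 may resume breastfeeding at a time read from one woman's milk, with no margin for slower clearance, no stated dose, no same-session result, and no stated lengthening of the hold if a later sample is positive

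*Combined protocol and SAP*

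**What the plan says.** Methods item 2 starts from a practical limit: "As real time testing of ketamine content in breastmilk is not possible". It therefore makes the first woman the reference for the rest: "the first subject will be the exemplar for the timing of the resumption of breast feeding based on the data obtained". The illustration is "such as not detectable at 9 hours, hence breast feeding may resume".

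The first woman has a fixed time: "For that first subject, breast feeding may resume at 18 hours". The plan justifies this hold by a half-life count, saying of the 18 h: "which corresponds to 9 half-lives for ketamine, 4 half-lives being the accepted timing for the absence of a molecule". No fixed time is written for the other three.

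The same item foresees that appreciable ketamine may still be present in a later subject at the last interval taken from the first subject's profile. The response it names is that "additional time frames for collection will be added". The feeding hold is not mentioned there.

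Other relevant text:
- Methods item 1, on the half-life: "The study will view the half-life as being a conservative 3 hours". The same item cites 2.1 h for ketamine, and the Summary of Research Design also reports 2.5 to 3 h.
- The Procedure Timing Chart gives 0.5 mg/kg in one session and 1.0 mg/kg in the second.
- The Informed Consent section says mothers will not breastfeed while the study lasts, in order to protect infants from exposure. It gives no number of hours.

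**The concern.** For the first subject, an undetectable sample is direct evidence about her own milk. For the other three it is evidence about someone else. The document states that no human milk data exist, and the Data Analysis section plans to relate milk concentration to age, weight, dose, milk volume and months of breastfeeding. Differences between women are therefore an open question in this study, and one woman's profile cannot bound the other three.

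A woman who clears ketamine more slowly than the first subject could, under the rule as written, feed milk that still contains drug. Her own assay would arrive afterwards. By then the only written response is more sampling. Her 0.5 mg/kg result might be available before her 1.0 mg/kg session, but the plan does not say it would be used.

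What is at stake is protection of the infants, which is the stated reason for withholding feeding. The concentration estimates do not depend on when feeding restarts.

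**Working it through.** **Inputs.** Half-lives: 2.1 h and a conservative 3 h (Methods item 1); 2.5 h as the lower end of the other range given (Summary of Research Design). Clearance standard: 4 half-lives (Methods item 2). Times: 18 h for the first subject and the 9 h example (Methods item 2).

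**Assumption.** Single-exponential decline in milk. Number of half-lives = t / h; fraction left = 0.5^(t/h); time to meet the standard = 4h. The half-lives are the plan's literature and design values, not a measured spread between women.

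**Step 1: the plan's own figure.** 18 / 2.1 = 8.57, which rounds to the stated 9. At the conservative value, 18 / 3 = 6.

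**Step 2: the 9 h example against the 4-half-life standard.**

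| Half-life | 4 half-lives | 9 h in half-lives | Left at 9 h |
|---|---|---|---|
| 2.1 h | 8.4 h | 4.29 | 5.13% |
| 2.5 h | 10 h | 3.6 | 8.25% |
| 3 h | 12 h | 3.0 | 12.5% |

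Four half-lives leave 0.5^4 = 6.25%. Nine hours meets the standard only for half-lives up to 9 / 4 = 2.25 h.

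**Step 3: an 18 h hold.** It meets the standard for half-lives up to 18 / 4 = 4.5 h. At 3 h it leaves 0.5^6 = 1.56%.

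**Step 4: the clock.** The chart puts the injection 15 minutes after the zero pump. A 9 h pump timed from zero is then 8.75 h after dosing: 8.75 / 3 = 2.92 half-lives, 13.2% left.

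**Step 5: incidental margins.** Methods item 3 says "Pumping of breast milk will be for a full expression so as not to influence concentrations in subsequent sampling intervals", so the next feed is newer milk. If that feed comes 0 to 3 h after a 9 h pump (assumption), the level at a 3 h half-life is 12.5% down to 6.25%, so the standard is at best just met. The 3 h sampling grid may add up to 3 h more, but only relative to the first subject's clearance.

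**Step 6: illustration of slower clearance.** Suppose the first subject has a 2.1 h half-life and just reaches the detection limit at 9 h. A later subject with the same starting level and a 3 h half-life reaches that limit at 9 × 3 / 2.1 = 12.9 h. At 9 h she is 12.5 / 5.13 = 2.4 times above it. If the time had been set at 0.5 mg/kg and used at 1.0 mg/kg, dose-proportional kinetics add one half-life: 12.9 + 3 = 15.9 h, and the ratio doubles to 4.9. An 18 h hold covers both cases; a 12 h hold covers neither.

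**The case against.** The best defence is that two tests are being compared. The plan uses 4 half-lives to justify the first woman's hold, before any milk data exist. For the others the test is a measured non-detect, and nothing says a data-based time must also satisfy 4 half-lives. That is fair, and it rules out several stronger readings that a reader might infer:

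- **That the plan fixes 9 h, or plainly breaks its own rule.** It does neither. Nine hours is an example that applies only if the first subject's sample is undetectable, and at 2.1 h it passes (8.4 h).
- **That 12.5% estimates what an infant would receive.** It does not. If that level were detectable in the first subject, 9 h would not be chosen. No detection limit, milk concentration or between-woman variability is given.
- **That a time from 0.5 mg/kg will be used at 1.0 mg/kg.** The text leaves this open, but dose-matched timing is the more natural reading: samples are labelled by dose and interval.
- **That calling 18 h nine half-lives is an arithmetic error.** It follows by rounding from 2.1 h. It only departs from the 3 h value.
- **That participants receive no feeding instruction.** The consent form was not available and may say more.

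The defence can also point to low oral bioavailability (about 20%, perhaps 10% in practice, and not infant figures) and to minimal data in Appendix A without reported infant harm, although that appendix also advises careful monitoring.

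What remains is the structure of the rule. A time taken from one woman is applied to three others with no margin, and a positive result in one of them is not linked to a longer hold. The objection does not answer that.

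**Conclusion.** The point holds as a gap in the resumption rule for subjects 2–4. They rely on one woman's profile, with no allowance for slower clearance, no stated dose and no same-session result. A positive last sample leads to more sampling but not, in the text, to a longer hold.

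Its size can be stated only against the plan's own standard. The 9 h example passes at 2.1 h and falls 3 h short at the conservative 3 h (12 h needed), under single-exponential decline. The percentages and the 12.9 h case illustrate that sensitivity; they do not estimate infant exposure, which cannot be derived from the document. The first subject's 18 h exceeds 12 h, so the shortfall does not apply to her. The milk concentration results are unaffected. This is a cheap safety improvement worth making.

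**What to change.** Amend Methods item 2 as follows:

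1. Make 18 h, timed from injection, the minimum hold for all subjects at both doses. Twelve hours is the least the plan's own figures support; 18 h is the time already accepted for the first subject.
2. If the first subject's 15 h sample at a dose is detectable, collect further 3-hourly samples, repeating the session if needed, as the item already allows. Set the hold at that dose for later subjects to at least 3 h after her first undetectable sample. (18 h is already 3 h after an undetectable 15 h sample.)
3. If any later subject's last sample is positive, lengthen the hold for all remaining sessions as well as adding collection times.

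**Cost of the 18 h minimum.** Three women at two doses make 6 sessions. Against an exemplar time of 9 h the extra hold is (18 − 9) × 6 = 54 h in total; against 12 h it is 36 h, and against 15 h it is 18 h. Milk expressed in those hours is discarded. Eligibility already requires a milk reservoir or bottle acceptance. This change needs no extra visits or assays. Sampling beyond 15 h, or a repeated session, would arise only if the first subject's 15 h sample were detectable.

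**Trade-off.** The study also asks whether a short pause in feeding is tolerable. With this change the Appendix C answers on tolerability would refer to an 18 h pause.

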1. 5) Each aliquot will be labelled with coded subject designation, concentration of ketamine administered, date, and interval. The lab will be provided with the actual quantity of ketamine administered to each subject at the 0.5 and 1.0mg/kg levels and the weight of each patient in kgs.
 - 1)
1. 6) The Lab will provide the data to KRF in formats suitable for journal publication.

INTAKE FORM ATTACHED

AS PREVIOUSLY INDICATED THERE ARE NO QUESTIONNAIRES BEING ADMINISTERED— THIS WAS DELETED FROM THE PRIOR REVISION

Inclusion Criteria

- Age 21-45
- Postpartum with established lactation for a minimum of 3 months.
- Ability to pump breast milk and to provide a reservoir for infant feeding prior to the study; or acceptance of bottle feeding by the infant.
- In good health—normal BP/P; afebrile-temp ascertained; review of systems by MD; absence of diagnosed illnesses.
- Not pregnant--Pregnancy tested for before each administration by urine assay.

Exclusion Criteria:

- Hypertension with a BP greater than 145/90
- Absence of all psychiatric medications specifically; medications and supplements, or evaluated by the PI for non-interference
- No alcohol or other substances such as marijuana for 72 hours or more.
- Weight <50kg or > 90kg.
- Pregnancy

Potential Adverse Effects

- • Nausea and vomiting—a less than 5% incidence of intolerability to ketamine.
- • Transient hypertension—BP will be monitored. In clinical practice, and in this age group, this has not occurred with any frequency.
- • Ketamine is a dissociative anesthetic and subjects have a high likelihood of experiencing dissociative effects during the first two hours following ketamine's administration. Generally, the major impact occurs in the first hour, with full recovery to baseline by 3 hours. The Investigators have conducted thousands of sessions in which dissociative effects are part of the ketamine assisted

psychotherapy (KAP) approach, including at much higher doses than those being administered in this study. Subjects may experience, an altered mental state in which there is an imaginative stream of associations, sensations and imagery. There can be anxiety accompanying a shift from ordinary reality. The Investigators have specialized in developing a transformative psychotherapy with utilization of this state and are fully equipped and experienced in dealing effectively with this state. Subjects will be prepared for the possibility of this

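### The lab receives dose, weight, date and interval with the samples while its low-level calls have no numerical limit; withholding dose and weight until concentrations are locked is a cheap partial safeguard

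*Combined protocol and SAP*

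**What the plan says.** **What the lab is told.** Methods, item 5: "Each aliquot will be labelled with coded subject designation, concentration of ketamine administered, date, and interval". The next sentence goes further: "The lab will be provided with the actual quantity of ketamine administered to each subject at the 0.5 and 1.0mg/kg levels", and it adds each woman's weight in kilograms. No section describes masking the lab, randomising run order or withholding dose or time.

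**What the lab does.** Methods, item 1: "Lab will prepare a standard for analysis of ketamine and its principle metabolite norketamine in breast milk". The measurement is therefore quantitative. No limit of detection or quantification is stated, and there is no rule for repeating an odd value.

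**What hangs on low readings.** Methods, item 2 contains four linked rules:
- For the first subject: "If there is a negligible quantity in the samples as the time frame proceeds, the lab will not analyze subsequent samples".
- For collection: "Breast milk will be collected until ketamine levels are undetectable".
- For adding time points: "If significant amounts of ketamine are found in samples from the 3 subsequent subjects at the last interval" set by the first subject, collection is extended.
- The first subject's data serve as the exemplar for later timing, illustrated as "such as not detectable at 9 hours, hence breast feeding may resume".

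None of the operative words in these rules has a number attached.

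**The concern.** Whoever decides that a late sample is negligible or undetectable will know the hour, the dose and the weight behind the tube. With a fixed numerical limit this would matter little. Without one, the call needs judgement, and the label tells the analyst what to expect.

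Two features give the call weight. First, a call of negligible can end the assays for that session, so later data may not be there to correct it. Second, the first subject's profile sets the sampling times for the other three women and is the reference for timing. With only 8 woman-sessions, one wrong call does not average out.

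Dose and weight enter the planned work only in the Data Analysis section, where concentrations are correlated with age, weight, dose, milk volume and months of breast feeding. That matrix is kept at the study site, so the lab has no stated need of them while it is measuring.

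**Working it through.** The plan states no figure on this point, so there is none to reproduce. The check has four parts.

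**1. Does the interval label tell the analyst what to expect?**
Inputs: half-life 2.1 h, and the 3 h the plan adopts as conservative (Methods, item 1); sampling to 15 h (Methods, item 2). Assumptions: single-exponential decline from time 0, with milk following these half-lives.
Fraction left = 0.5^(t / half-life):

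| Time | 2.1 h half-life | 3 h half-life |
|---|---|---|
| 9 h | 5.1% | 12.5% |
| 12 h | 1.9% | 6.25% |
| 15 h | 0.7% | 3.1% |

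Late samples are expected to be low, and the label says which samples are late.

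**2. How much does the dose label add?**
If concentration is proportional to dose, C = kD × 0.5^(t / h), and the time to reach a fixed limit L is h × log2(kD / L). Doubling D adds exactly one half-life h, that is 2.1 to 3 h. This is at most one 3 h sampling interval. At 15 h with a 2.1 h half-life, the higher dose would stand at 2 × 0.7% = 1.4% on the lower dose's scale. So the true dose difference in time to non-detection is no larger than one step of the sampling grid, and one changed call is at least one step. This is the consequence of a wrong call. It does not estimate how often one would occur.

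**3. Can the direction of a bias be derived?**
No. An analyst who expects decline might call a late low positive blank, which shortens the apparent time. An analyst who expects the higher dose to persist might call a doubtful high-dose sample positive, which lengthens the time and widens the dose contrast. The document does not favour either.

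**4. What would masking cost in assays?**
Inputs: 4 women, 2 sessions each, 6 time points (0 to 15 h) on the first-subject schedule.
- All samples on that schedule: 4 × 2 × 6 = 48.
- Assays stopped after the 9 h sample in every session (0, 3, 6, 9 h): 8 × 4 = 32. Difference: 48 − 32 = 16.
- If the other three women are sampled only to 9 h, the samples collected number 1 × 2 × 6 + 3 × 2 × 4 = 36, and the difference from 32 is 4.

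So masking the interval by assaying everything costs 4 to 16 assays more than stopping after 9 h, depending on the schedule used. Withholding dose and weight alone costs no assays beyond an occasional re-run.

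**The case against.** **The readout is a quantitative assay, not a graded opinion.** This stands. It confines the concern to readings near the limit. The room for judgement comes mainly from the undefined terms, so a numerical limit is an essential part of any remedy; random labels alone would leave the calls undefined.

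**Subject identity is already masked.** This stands. A reader might infer from item 5 that the analyst knows the woman, but the label carries a coded designation, and Procedures and Data Storage both provide for coded identifiers.

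**The plan does not show that results would be biased in a known way.** This stands. A reader might infer that open labels would shorten the time to non-detection and flatten the contrast between doses. The document does not support this: an expectation that high-dose samples stay positive would act the opposite way.

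**Coding cannot fully hide the dose.** This stands. The Procedure Timing Chart gives 0.5 mg/kg first and 1.0 mg/kg at the second session, at least 3 days apart, and aliquots go to the lab promptly. Date or arrival order can reveal the dose. Where tubes are released in pump order at fixed 3 h spacing, the order is the interval, and the first tube is recognisably the pre-dose sample.

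**The lab needs the information for its tasks.** This stands in part. The stopping rule needs time order, rapid processing is wanted for the first subject, and Methods, item 6 asks the lab for publication-ready output. None of these needs dose or weight before concentrations are final.

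**The study is small and descriptive, with no formal test.** This is true, and it keeps the point minor.

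**Conclusion.** The concern holds as a possible measurement bias that is easily reduced. It is confined to calls near the assay limit and to the decision to leave later samples unassayed. It rests on three facts in the document: dose, weight, date and interval are open to the lab; no numerical limit governs the low-level calls; and the lab may stop assaying on the strength of such a call.

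The size and direction of any effect are unknown. One changed call shifts a session's apparent time to non-detection by at least 3 h, in a study of 8 sessions. Comparing that shift with the dose difference rests on dose proportionality and on milk following the quoted half-lives, neither of which has been established for milk.

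A reader might also infer that coded labels would remove the problem at almost no cost. They would not remove it, because session order, arrival dates and pump order still carry information. The low cost applies to dose, weight and date; full masking of the interval conflicts with the stopping rule unless the procedure changes. This is a worthwhile improvement and does not invalidate the measurements.

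**What to change.** 1. Label tubes with a random sample code. Keep dose, weight and date in the study-site file, and release them to the lab only after concentrations are returned and locked. The lab can then prepare the item 6 output.
2. Before any assay, state a numerical detection or quantification limit for ketamine and norketamine. Apply it to every sample in place of the three undefined terms. This is a measurement rule only; what level matters for resuming breast feeding is a separate clinical question.
3. Choose one route for the interval:
   - If the rule that "the lab will not analyze subsequent samples" is kept, have the site release tubes in pump order without dose or weight. This also suits rapid processing for the first subject.
   - Otherwise assay every collected sample and mask the interval too, with the pre-dose samples among the coded tubes as blanks.
4. State in the plan that masking is partial.

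Cost: a code list, a later merge and an occasional dilution and re-run when a sample is over range. Only if everything is assayed are there extra assays: 16 on the full first-subject schedule, compared with stopping after 9 h in every session.
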